The investigator will permit a representative of the sponsor or the sponsor's designate and the FDA, if requested, to inspect all case report forms and corresponding portions of the study subjects' original office, hospital and/or clinic medical records at regular intervals throughout the study. These inspections are for the purpose of assessing the progress of the study, verifying adherence to the protocol, determining the completeness and exactness of the data being entered on the case report forms. During on-site visits, case report forms will be examined by the study monitor(s) and the data verified by comparison with corresponding source data (such as clinic, hospital and/or office records). Due to the geographic distance of the clinical site from the sponsor, phone conferences or teleconferences may be used to complete the monitoring requirement.

Final Report

Following the completion of the study, the Investigator shall prepare a final study report. The final report will include a general description of the conduct of the study including protocol deviations, subject withdrawals, discussion of any adverse events, safety and efficacy data, laboratory data, and statistical analysis of the data if available. This report will be approved and signed by the Principal Investigator.

Record Retention and Access to Source Data/Documents

Source documents must be kept for at least six (6) years after terminating the study. The Investigator will maintain all study documentation for all subjects entered into the study in a secure area ensuring the confidentiality of the information collected. Securing records includes placing written forms in locked file cabinets and/or sealed and labeled storage boxes in a locked room.

References

- 2 Hooper, L.V., et al., Molecular analysis of commensal host-microbial relationships in the intestine. *Science*, 2001. 291(5505): p. 881-4.
- 3 Macpherson, A.J. and N.L. Harris, Interactions between commensal intestinal bacteria and the immune system. *Nat Rev Immunol*, 2004. 4(6): p. 478-85.
- 4 Xu, J. and J.I. Gordon, Inaugural Article: Honor thy symbionts. *Proc Natl Acad Sci U S A*, 2003. 100(18):p. 10452-9.

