Exclusion criteria:

- Medical condition which requires premedication prior to dental treatments/visits
- Subjects unable or unwilling to undergo informed consent process.
- Subjects currently using anti-gingivitis oral rinses (washout period of 1 week)
- History of periodontal disease
- History of systemic inflammatory or immune conditions
- Use of antibiotic or anti-inflammatory drugs within 30 days of enrollment
- Pregnant or breastfeeding at time of screening
- Concurrent orthodontic treatment
- Untreated carious lesions and/or inadequate restorations, implants, crowns on maxillary non-molar teeth
- Participation in any other clinical study or test panel within 1 week prior to enrollment into this study
- Use of tobacco products
- Subjects who must receive dental treatment during the study dates
- Orthodontic bands, appliances, or crowns and bridges, or removable partial dentures affecting the non-molar maxillary teeth
- Immune compromised individuals (HIV, AIDS, immuno suppressive drug therapy)

[figure not shown]
METHODS

Induced Gingivitis Model

In each participant, one maxillary quadrant will be assigned as test quadrant (experimental gingivitis) and contralateral quadrant as control quadrant. Assignment of quadrants will be random using a computer program for randomization.

At the initial visit all participants will undergo the informed consent process, with thorough discussion of study participation details. Full clinical assessments, biospecimen collections and imaging will be performed and maxillary impression will be taken for acrylic stent. Maxillary acrylic stents will be fabricated to cover teeth on test quadrant extending at least 4-5 mm apical to the marginal gingiva both buccal and palatal and will be relieved around interproximal areas to prevent plaque disturbance. An oral prophylaxis will be administered and thorough oral hygiene instructions will be given. Participants will return 14 days after this initial visit and will have baseline measurements and biospecimen collections taken. These measurements include an abbreviated health assessment with a periodontal probe to measure pocket depths, gingival and plaque index and Imaging of the buccal gingival on eight maxillary teeth (#'s 5-12), and collection of crevicular fluid and plaque samples³⁷.

UW - Colgate Imaging Study

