At the baseline visit the acrylic stent will be given to participant with detailed instructions for use. Participants will be given instructions not to brush teeth on test quadrant (under the provided stent) and not to use any other measure of oral hygiene (flossing, interdental aids, xylitol gum, and mouth rinses). Participants will be provided with Colgate Cavity Protection Toothpaste and a soft bristle toothbrush to use during their entire participation in this study. In order to prevent accidental brushing of the experimental sites, subjects will be asked to wear the maxillary stent during regular brushing. Participants will be

Confidential

rechecked at Day 2, 4, 7 & 14 and a full assessment of their plaque and gingival status will be carried out, specimens collected, and imaging performed each time using the same criteria as at the baseline examination. The course of the "no-brushing" part of the experiment will last up to 14 days to allow all the participants to develop gingivitis. Following clinical assessment and biospecimen collections at day 14, a thorough prophylaxis will be administered.

Participants will be given detailed instructions in oral hygiene methods using a manual toothbrush and Colgate Cavity protection toothpaste. Subjects will also use dental floss beginning the same day and continuing once in the morning and once at night for the duration of the study. Assessment of plaque and gingival condition along with imaging will continue during the entire reversal phase, Day 21 and Day 28. At a point where the Gingival Index and Plaque Index scores approach zero (approximately day 28), all measurements and biospecimen samples will be taken, along with imaging and that visit will be recorded as end-of-study.

Medical imaging device

The medical imaging device is a home-built multi-functional OCT system (MI-OCT), which is also illustrated in Figure 1. The functionality of the system includes:

- Anatomical structure imaging (OCT)
- Functional angiography (OCTA)
- Molecular imaging: Red and green autofluorescence imaging (MI)

The components of the system include:

- A laser light source (NIR, 1300nm peak, 100nm bandwidth, peak power 3.5mW)
- Optical components that transmit OCT light beam into biological tissue, including: optical fiber and optics table, galvanometer mirror scanners, and several other optics components (lenses, dichroic mirrors, prism, etc.)
- CMOS camera for molecular imaging (MI)

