Sub-gingival plaque will be collected using sterile paper points inserted in the gingival sulcus for 30s from the mesiobuccal and mesiodistalsurfaces of teeth #'s5- 12. Plaque samples will be placed in micro centrifuge tubes then transported on ice to -80oC freezer in lab.

Analysis of GCF chemokines

GCF samples will undergo assay of 3 angiogenesis chemokines using commercially available kits. The following list of chemokine will be analyzed: angiopoietin-1, vascular endothelial growth factor, and hypoxia-inducible factor 1 alpha. The expression of these chemokines have all been shown to contribute to angiogenesis and possibly homeostasis in gingival tissue. Commercially available ELISA kits will determine the concentration of Myeloperoxidase (MPO).

Analysis of microbial composition

Plaque samples will be stored in the Periodontics Repository for future studies. The samples will not be analyzed as part of this study.

Imaging

1) Autofluorescence imaging

Autofluorescence images are captured and analyzed for two purposes:

- a. Plaque (biofilm) detection (red autofluorescence)
- b. Enamel absorption and anomalies (green autofluorescence)

The images are registered in each subsequent visit. This registration step allows observation on the progression of a) plaque and b) tissues response over the whole study period.

2) OCT and OCTA

Data is captured for each visit and is analyzed off-line. The following features are extracted and monitored:

- a. The rete-ridges structure (OCT) in free gingiva. During inflammation, the rete-ridges layer becomes thinner and is replaced by connective tissues.
- b. The depth of the free gingiva (OCT+OCTA), which is defined by a line joining: i) the

Confidential

surface of the gingiva, ii) projected perpendicular to the gingival sulcus line, and iii) passing through the point where connective blood vessels in free/attached gingiva disappear

- c. The vasculature (OCTA) in the free gingiva.
- d. Possible changes in other morphology (reserved for exploratory parameters).

Recovery and Termination from the Study

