APPENDIX B

Protocol Title	Induced Gingivitis and Intra-oral Imaging
Study Duration	Approximately 42 days total 14 day “no brushing” period
Pre-experimental (Hygiene) phase (Day -14 to 0) Visit at Day -14	
At Day -14 visit:
 
 • Screening (may be done at separate visit) • Informed Consent • The following measurements will be taken on six surfaces of all teeth 
 ○ Plaque Evaluation ○ Gingival Index Evaluation ○ Probe pocket depths ○ Attachment Level ○ Bleeding on Probing • The following Biospecimen will be taken from mesiobuccal and mesiopalatal surfaces of teeth #'s 5- 12, 
 ○ Gingival Crevicular Fluid ○ Plaque sample • Prophylaxis (scaling and polishing) • Oral hygiene instructions • Impression for maxillary stent
Baseline Visit at Day 0	
 • The following measurements will be taken from mesiobuccal and mesiopalatal surfaces of teeth #'s5- 12 
 ○ Plaque Evaluation ○ Gingival Index Evaluation ○ Probe pocket depths ○ Attachment Level ○ Bleeding on Probing ○ Gingival Crevicular Fluid ○ Plaque sample • Stent will be delivered • Imaging buccal gingival teeth #'s 5 - 12 • Begin oral hygiene abstinence

Protocol Number CRO-2018-06-EXG-JG

Confidential

Gingivitis induction phase (14 Days) Visit at Day 2 Visit at Day 4 Visit at Day 7 Visit at Day 14	Assessments over 14 days (4 visits) 
• The following measurements will be taken from mesiobuccal and mesiopalatal surfaces of teeth #'s 5- 12
○ Plaque Evaluation○ Gingival Index Evaluation○ Probe pocket depths○ Attachment Level○ Bleeding on Probing○ Gingival Crevicular Fluid○ Plaque sample• Imaging buccal gingival teeth #'s 5 - 12• At Day 14 after data collection:
○ Prophylaxis (scaling and polishing)○ Reinstitution of regular oral hygiene
Resolution Phase (14 Days) Visit at Day 21 Final Visit at Day 28	
• The following measurements will be taken from mesiobuccal and mesiopalatal surfaces of teeth #'s 5- 12
○ Plaque Evaluation○ Gingival Index Evaluation○ Probe pocket depths○ Attachment Level○ Bleeding on Probing○ Gingival Crevicular Fluid○ Plaque sample• Imaging buccal gingival teeth #'s 5 - 12

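### The protocol does not secure imaging before the gum margin is probed and sampled, and its own listings of the order disagree

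*Combined protocol and SAP*

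**What the plan says.** The order of work within a visit has to be pieced together from the Methods (Induced Gingivitis Model) and Appendix B.

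- **Initial visit (Day -14), Methods:** "Full clinical assessments, biospecimen collections and imaging will be performed". Appendix B lists no imaging at this visit.
- **Baseline (Day 0), Methods:** probing and the indices come first, then "Imaging of the buccal gingival on eight maxillary teeth (#'s 5-12), and collection of crevicular fluid and plaque samples". Appendix B instead lists the indices, probing, bleeding, GCF and the plaque sample, then "Stent will be delivered", and only then imaging.
- **Days 2, 4, 7 and 14, Methods:** "a full assessment of their plaque and gingival status will be carried out, specimens collected, and imaging performed each time". Appendix B agrees: "Imaging buccal gingival teeth #'s 5 - 12" follows the block of clinical and specimen items.
- **Days 21 and 28, Methods:** "Assessment of plaque and gingival condition along with imaging will continue during the entire reversal phase, Day 21 and Day 28", which sets no order. Appendix B again puts imaging after the clinical and specimen items.

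Outcomes states one order among the measurements, which is plaque index before GCF. GI is scored with air and a probe. GCF is taken on a paper strip left in the crevice for 30 seconds. Under Plaque collection, "Sub-gingival plaque will be collected using sterile paper points inserted in the gingival sulcus for 30s". The imaging is then read for plaque (red autofluorescence) and for the vessels of the free gingiva (OCTA).

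**The concern.** Outcomes sets the question as the sensitivity and specificity of the imaging against GI and GCF volume. In such a study the index test should not be altered by the reference test, least of all in a way that depends on the reference result.

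On the GI scale, score 1 means no bleeding on probing, score 2 includes bleeding on probing, and score 3 includes a tendency to bleed spontaneously. If probing comes first, obtaining the reference score provokes bleeding at the sites that the score will call inflamed. The OCTA scan then looks for vascular change at those margins. Strips and paper points in the sulcus may also disturb plaque before it is imaged. Such a disturbance would differ between test and control quadrants and would change over time, so it would not average out. The background section presents the method as a non-invasive examination, and a scan taken after probing does not test that use.

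**Working it through.** The plan gives no figure to reproduce here. The check sets the listings side by side and adds arithmetic on the stated scan times.

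**Step 1. Position of imaging in each listing**

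| Visit | Methods narrative | Appendix B |
|---|---|---|
| Day -14 | after assessment and specimens | no imaging listed |
| Day 0 | after probing, before GCF and plaque | after probing, GCF, plaque and stent delivery |
| Days 2, 4, 7, 14 | after assessment and specimens | after probing, GCF and plaque |
| Days 21, 28 | no order given | after probing, GCF and plaque |

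Appendix B has 7 imaging visits (Days 0, 2, 4, 7, 14, 21, 28), with imaging after the contact measurements at all 7. Wherever an order can be read, probing precedes imaging. Sampling precedes imaging in every ordered listing except the Day 0 narrative. No text sets an interval after probing. GCF strips visibly contaminated with saliva and blood are excluded, but there is no corresponding rule for images.

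**Step 2. Which sites overlap**

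Probing and GCF sampling use mesiobuccal and mesiopalatal sites on teeth 5 to 12. Imaging covers buccal gingiva only, so the overlap is at the mesiobuccal sites. Plaque collection is staggered between sites, so a given margin need not receive a paper point at each visit.

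**Step 3. When provoked bleeding could matter**

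Day 0 eligibility requires GI of at most 0.5 and no bleeding on probing. The Methods expect GI near zero at about Day 28. Provoked bleeding would therefore fall mainly in the test quadrant during induction, and perhaps at Day 21.

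**Step 4. Baseline against follow-up**

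A site that follows the Methods narrative would scan before sampling at Day 0 and after sampling at Days 2 to 14. Change from baseline would then mix the effect of gingivitis with that of a changed procedure.

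**Step 5. Time since probing (Imaging procedure)**

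- Per scan site: positioning 1 to 3 min, autofluorescence 2 to 3 min, OCT under 1 min.
- Lower bound: 1 + 2 = 3 min, plus the OCT scan. Upper bound: 3 + 3 + 1 = 7 min.
- Six scan sites: 6 × 3 = 18 to 6 × 7 = 42 min.
- First to last scan site, five sites apart: 5 × 3 = 15 to 5 × 7 = 35 min.

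If all probing is finished before imaging starts, the last site is scanned about 15 to 35 minutes later after probing than the first, apart from differences in when each site was probed. Nothing in the plan controls this.

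**The case against.** The strongest reply is that a list is not a running order, and these lists show it. At Day -14 Appendix B puts the stent impression after the prophylaxis. The Methods mention it before, and Tooth Stent Construction has the shields made before the prophylaxis. Where order matters, the protocol says so: plaque index before GCF, and the Day 14 prophylaxis after data collection. This stands. What is shown is an unfixed and inconsistent order, and any bias depends on a site following the lists.

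A reader might infer that at every visit, and at every scan site, the scan records tissue that has just been made to bleed and plaque that has just been disturbed. The documents do not support that. The Day 0 narrative lists imaging before sampling, the Day 21 and 28 narrative is neutral, palatal sites are not imaged, and bleeding should be largely absent at Day 0. The six scan sites are not mapped to the probed points. The documents also say nothing about how long provoked bleeding lasts, how it affects OCTA or autofluorescence images, or how much visible plaque a paper point removes.

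It can also be said that imaging first is not free. The scan uses a retractor and bite bar, and GCF volume is itself a comparator, so a long scan beforehand could affect it. That is fair and has to be managed. Finally, this is a pilot of up to 15 people. Its size does not help, because images of undisturbed tissue cannot be recovered in the analysis.

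**Conclusion.** The point holds as a gap in the protocol: nothing secures imaging before contact measurements, most listings put it after them, and the two Day 0 listings conflict. If the listed order is followed, the disturbance tracks the reference standard at the shared mesiobuccal margins, mainly in the test quadrant during induction. It could raise or lower apparent sensitivity and specificity. Its size cannot be derived from the documents, and no percentage should be attached to it. The conclusion assumes that sites work roughly in the listed order and that probing or sampling can alter what the scan records. The second assumption is plausible but not documented. I class this as a cheap improvement, worth making before the first participant is scanned.

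**What to change.** Reconcile the Day -14, Day 0, induction and resolution text in the Methods with Appendix B, including whether imaging takes place at Day -14. State one order for every imaging visit:

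1. Autofluorescence and OCT/OCTA imaging, before any air, probe, strip or paper point touches the margin.
2. Visible plaque index.
3. GCF collection.
4. GI, then probing depth, attachment level and bleeding on probing.

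Take the banked plaque sample, which this study does not analyse, only after imaging and GCF. The order keeps the existing rule of plaque index before GCF. It also takes GCF before probing, whereas Appendix B lists bleeding on probing first. The listed order could lose blood-contaminated strips selectively at inflamed sites.

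The cost is a change to the protocol text and the visit worksheet, with no new procedure. The downside is that GCF is collected after a scan of roughly 18 to 42 minutes with a retractor in place. Keep that sequence the same at all visits and in both quadrants, so that any effect on GCF volume is common to the comparisons.

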**Induced Gingivitis & Intra-oral Imaging
Protocol Number CRO-2018-06-EXG-JG**

ClinicalTrials.gov ID: NCT03750955

Protocol Date: July 18, 2018

Sponsored by:

Colgate-Palmolive Technology Center
[name]
[name]

Protocol Approval

Signature Page

[name]
Vice President and Chief Dental Officer

Date

[name]
Word Wide Director – Oral Care Clinical Research

Date

Confidential

Protocol Number CRO-2018-06-EXG-JG

Induced Gingivitis & Intra-oral Imaging
Protocol Number: CRO-2018-06-EXG-JG

Sponsored by:

Dental Clinical Research
Colgate-Palmolive Technology Center
[name]
[name]

Protocol Approval

PRINCIPAL INVESTIGATOR APPROVAL AND AGREEMENT

I, the undersigned, have reviewed this protocol and I agree to conduct this protocol in accordance with the Guidelines for Good Clinical Practice, the ethical principles set forth in the Declaration of Helsinki, and with the U.S. Code of Federal Regulations governing the protection of human subjects (21 CFR 50) and the institutional review boards (21 CFR 56).

[name]
Principal Investigator

Date

Confidential

STUDY AIM:

To evaluate the ability of an intra-oral imaging device to assess the level of gingival inflammation present and the process of resolution using a localized experimentally induced gingivitis model.

BACKGROUND AND SIGNIFICANCE:

This project is significant for public health because it aims to validate a non-invasive imaging examination for determining gingival (gum) inflammation. Given that the prevalence of gingivitis in the US population is greater than 50%, and that gingivitis can progress to periodontitis and tooth loss if left untreated, the proposed non-invasive imaging method can be an invaluable asset in clinicians' quivers for the early prevention of this prevalent disease.

STUDY DESIGN

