This study is a modification of classical experimental gingivitis model. The study will prospectively enroll subjects and a maxillary sextant to an intervention, while the other sextant will serve as control in a split-mouth design of localized experimental gingivitis, utilizing localized stent-induced biofilm overgrowth model (SIBO). The intervention will consist of cessation of oral hygiene versus an active control of oral hygiene with a fluoridated toothpaste that will be provided by the investigators. The intervention, i.e. oral hygiene cessation will manipulate the participants' oral environment by leading to reversible inflammation of the gingival tissues. This is a well established protocol that was first introduced in 1965 (Loe's experimental gingivitis) and is safe, reliable and widely utilized in periodontal clinical trials. The purpose of this study is to evaluate the effects of oral hygiene cessation in the gingival tissues by an innovative non-invasive microimaging technique, i.e. OCT.

The study will include the following phases – 1) Hygiene phase of 2 weeks; 2) Gingivitis induction phase with stent lasting up to 2 weeks; and 3) Resolution phase of 2 weeks. This pilot study will enroll up to 15 generally healthy adults aged 18-35 years that are self-referred or referred to the UW School of Dentistry. Recruitment will be completed in 3 waves. The study will include an oral health history review, probing depths, plaque & gingival evaluations, biospecimens collection and imaging of the buccal gingiva of teeth #5 - 12.

RECRUITMENT

All study participants will be patients of record at the UW School of Dentistry, or referred. All study participants will undergo informed consent process, prior to enrollment in the study. Categorization of participants and sites will be based on the clinical assessments. Other than the study-related oral health history recorded, there is no intention to obtain information from the participants' other dental or medical records. The first participant will be assigned a number, and all the following subjects will be assigned consecutive numbers by accession.

Inclusion criteria:

- Aged 18-35 years
- In good general health, ASA I
- No clinical signs of gingival inflammation at >90% sites observed
- Probing Depth(PD) \leq 3.0 mm
- Attachment Loss (AL) = 0 mm
- Gingival health at baseline visit (Day 0): Gingival Index (GI) \leq 0.5, Bleeding on probing (BOP)(-)
- Non-smokers
- Fluent in English

Confidential

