In the present study, we will be examining the sensitivity, specificity, and practicality of a new microimaging technique for assessing experimental gingivitis, as compared with standard health-related biomedical outcomes (i.e. gingival index and gingival crevicular fluid volume).

Abbreviated periodontal health assessment

Clinical data will be documented based on probing depth (PD), visible plaque index (VPI), gingival index (GI) and bleeding on probing (BOP)³⁸. All clinical measurement will be conducted using a manual periodontal probe. BOP will be recorded within 20 seconds of probing. The following four maxillary teeth will be used in each test and control quadrant: first premolar – central incisor. For each tooth, all measurements and biospecimen collection will be taken on mesiobuccal and mesiopalatal surfaces. Staggering of sites (mesiobuccal & mesiodistal) will be performed for plaque collection.

Visible Plaque Index

The surfaces of the study teeth will be scored and given either a "0" no plaque or "1" plaque assessment:

0 = No plaque

1 = Visible Plaque

Confidential

Loe and Silness Gingival Index (GI)

The surfaces of the study teeth will be evaluated using light air and a periodontal probe. A score is given based on the following scale:

0 = Normal gingiva

1 = Mild inflammation, slight change in color, slight edema, no bleeding on probing

2 = Moderate inflammation, moderate glazing, redness, bleeding on probing

3 = Severe inflammation, marked redness and hypertrophy, ulceration, tendency to spontaneous bleeding

Gingival Crevicular Fluid (GCF) collection

Prior to GCF collection the plaque index will be recorded. The sites to be sampled will be isolated with cotton rolls and gently air-dried. GCF samples will be collected with sterile paper strips (Periopaper strips, Oraflow Inc.) that will be inserted into the gingival crevice until mild resistance is felt and left in place for 30 seconds.

Amount of GCF samples collected will be quantified with a Periotron 6000 (Oraflow, Inc.) and will be expressed in microliter.³⁹ GCF will be collected from the mesiobuccal and mesiopalatal surfaces of teeth #'s 5- 12. Paper strips visibly contaminated with saliva and blood will be excluded from the study. All samples will be collected in micro centrifuge tubes. They will be transported on ice and stored within 24 hours at -80oC until processing.

Plaque collection

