A label with the subject's ID and the date of preparation is affixed to the buccal surface, and then 1-mm-thick mouthguard material is vacuum-adapted over the toothshield and trimmed to the original contours. The shields are prepared prior to the prophylaxis, chemically disinfected, and packed in individual plastic bags with each subject's name.

Statistical Analysis Plan

Multiple sites within each subject will be evaluated using a Gingival Bleeding Index at baseline and subsequent timepoints during clinical exams. The gingivitis bleeding scores will be averaged to provide a mean score per subject for each exam period. Product means and standard deviations will be calculated for each time period. Analysis of Variance techniques (possibly including Analysis of Covariance using the baseline scores as the covariant) will be used to compare the difference between the two test treatments using the 95% confidence level ($p \leq 0.05$).

Based upon our initial study the selection of 15 participants is expected to identify statistically significant differences in clinical parameters, GCF chemokines level, MPO expression and microbial composition over time among the subjects of the study. Participants will be enrolled in cohorts of 5 and we have planned for 3 waves to reach the final sample size $N=15$.

Confidential

REPORT OF ADVERSE REACTIONS

Subjects will be told of any possible adverse reactions or side effects from lack of oral hygiene and stent use, i.e. oral irritation. At the all clinic visits/examinations each participant will be asked if they have experienced any discomfort or oral irritation. In addition, all subjects will be examined for signs of epithelial desquamation (sloughing) and discoloration of the teeth and/or tongue. The investigators will record any and all adverse reactions. If the evidence indicates that the adverse reaction may be due to lack of oral hygiene, the subject will be instructed to resume oral hygiene and appropriate treatment will be provided. If an adverse event occurs it is expected to be mild and abate (stop) when oral hygiene is resumed. In the event of an adverse experience, emergency or other problems or questions regarding participation in this study subjects will be advised to contact the following investigator(s):

[name]
Office: [contact]

In the event of a medical emergency, subjects will be instructed to contact their physician.

Definitions

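### The stated question is the imaging device's sensitivity and specificity, but the analysis plan gives a method only for a clinical bleeding score

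*Combined protocol and SAP*

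**What the plan says.** The Study Aim is "To evaluate the ability of an intra-oral imaging device to assess the level of gingival inflammation present", together with its resolution. The Outcomes section turns this into accuracy measures: "we will be examining the sensitivity, specificity, and practicality of a new microimaging technique for assessing experimental gingivitis". The comparators it names are GI and GCF volume.

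The Statistical Analysis Plan section does something else. Bleeding scores are averaged per subject at each examination, and ANOVA, possibly ANCOVA on baseline, "will be used to compare the difference between the two test treatments" at p ≤ 0.05. The sample-size paragraph then lists clinical parameters, GCF chemokines, myeloperoxidase and microbial composition as expected to differ over time. It gives no method for them, and imaging is not on the list.

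On the images, the OCT and OCTA paragraph says: "Data is captured for each visit and is analyzed off-line. The following features are extracted and monitored". The features are rete-ridge structure, depth of the free gingiva, its vasculature, and other morphology held for exploration. No summary measure, threshold or comparison follows.

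On the reference, the Recruitment section says: "Categorization of participants and sites will be based on the clinical assessments". The GI thresholds in the documents serve entry (0.5 or less at Day 0) and the early move to resolution (score 3 in at least 25% of experimental teeth). None classifies a site as positive or negative for an accuracy table.

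**The concern.** Comparing bleeding between the hygiene-cessation and control quadrants is a positive control. The Study Design section itself describes the model as well established and dates it to 1965, so a significant result would show that gingivitis was induced. It would not show that the device detects it. The bleeding index is also not one of the two comparators that the Outcomes section names.

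At stake is the study's only stated aim. With no prespecified imaging feature, device threshold, reference cut-off or site pairing, each could be settled once the data are known, and accuracy figures obtained that way tend to flatter the device. An undefined imaging order and an unmasked reading would be further routes to biased agreement.

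**Working it through.** **1. Question against analysis.**

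| Element needed for sensitivity and specificity | What the documents give |
|---|---|
| Index variable | Several OCT/OCTA features; none chosen, no threshold |
| Reference variable | GI and GCF volume named; no cut-off |
| Unit and pairing | Not defined |
| Estimator and interval | None for imaging |
| Several sites per subject | No method beyond averaging the bleeding score |

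**2. Site pairing.** Clinical measurements are mesiobuccal and mesiopalatal on four teeth per quadrant: 4 × 2 = 8 sites per quadrant, of which 4 are buccal. Imaging is of the buccal gingiva of teeth 5 to 12, which is 8 teeth, but the Imaging procedure section has 6 scan sites in total. Palatal sites have no image, and 8 buccal sites do not map one-to-one onto 6 scans.

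**3. Order and masking.** For Days 2 to 14 the Induced Gingivitis Model section says "a full assessment of their plaque and gingival status will be carried out, specimens collected, and imaging performed each time", with imaging last. Appendix B also lists imaging after sampling at Days 0 to 28. The baseline description in the Induced Gingivitis Model section, however, lists imaging after probing and the indices but before fluid and plaque collection. The accounts of the baseline visit therefore differ. No section says whether the off-line reader knows quadrant, visit or clinical score.

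**4. Precision of the missing estimate.** There is no figure in the plan to reproduce: N = 15 comes with no effect size, SD, power or precision target. The following is illustrative.

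Inputs from the documents: 15 subjects; 4 buccal test sites per subject (four teeth), or 3 if the 6 scan sites split evenly between quadrants (assumption). Further assumptions: sensitivity p = 0.85; all imaged test sites reference-positive at Day 14; intraclass correlation (ICC) 0, 0.2 or 0.6.

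With m sites per subject, N = 15m, design effect DE = 1 + (m − 1) × ICC, n_eff = N / DE, and half-width = 1.96 × √(p(1 − p) / n_eff), where p(1 − p) = 0.85 × 0.15 = 0.1275.

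| m | N | ICC | DE | n_eff | 95% half-width (points) |
|---|---|---|---|---|---|
| 4 | 60 | 0 | 1.0 | 60.0 | 9.0 |
| 4 | 60 | 0.2 | 1.6 | 37.5 | 11.4 |
| 4 | 60 | 0.6 | 2.8 | 21.4 | 15.1 |
| 3 | 45 | 0 | 1.0 | 45.0 | 10.4 |
| 3 | 45 | 0.2 | 1.4 | 32.1 | 12.3 |
| 3 | 45 | 0.6 | 2.2 | 20.5 | 15.5 |

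If some test sites are not reference-positive at Day 14, N falls and every half-width grows.

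**The case against.** The strongest reply is that this is a pilot of up to 15 people, that the comparators are named, that sites are to be categorised clinically, and that images are taken at seven visits from Day 0 to Day 28. The data for an accuracy analysis will therefore exist. All of that is true, and it supports labelling the analysis exploratory. It does not supply the analysis: a pilot may be imprecise, but it should still say how its aim will be estimated.

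Several stronger readings are tempting, and the documents do not support them.

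- A reader might infer that there is no reference standard at all. GI and GCF volume are named; the cut-off is what is missing.
- A reader might infer that imaging always follows probing and sampling. The baseline description puts imaging before sampling, and the lists read as inventories, not a mandated sequence. The supportable point is that the order is inconsistent and unset.
- A reader might infer that the image reader is unmasked. The documents are silent on this.
- A reader might infer that all sites and visits will be pooled as independent. No section plans such a table.

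Two practical objections also stand. The autofluorescence images are registered from visit to visit, so visit cannot always be hidden. Scanning is also long. Per site it takes 1–3 minutes for positioning, 2–3 for autofluorescence and under 1 for OCT, so six sites take roughly 6 × 3 = 18 to 6 × 7 = 42 minutes with a retractor in place. The documents do not say whether that affects GCF volume measured afterwards.

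**Conclusion.** The concern holds and should be fixed before analysis: the sole aim has no planned analysis, and the one comparison with a method checks the model, not the device. It would go too far to say that the device question cannot be answered, because the images will exist. What is missing is prespecification.

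On the stated assumptions (sensitivity 85%, 3 or 4 imaged test sites per subject, all reference-positive at Day 14), the 95% half-width is about 9 to 10 points with sites treated as independent and about 11 to 15 points at ICC 0.2 to 0.6. The sensitivity, the ICCs and the all-positive condition are not document values. The absence of an imaging analysis does not depend on them.

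**What to change.** Add to the Statistical Analysis Plan a primary imaging analysis, labelled pilot/exploratory.

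- **Index.** Name one feature from the OCT and OCTA list, for example free-gingiva vasculature, with a defined summary measure. Make the others secondary.
- **Reference and pairing.** Map each scan site to a mesiobuccal clinical site and exclude palatal sites. Prespecify the GI cut-off, for example GI ≥ 2, and also report GI ≥ 1, because the protocol's scale defines GI 1 as mild inflammation. The particular feature and cut-off are choices; what is required is fixing them in advance.
- **Estimates.** Report AUC, and sensitivity and specificity at a device cut-off chosen by leave-one-subject-out, with 95% intervals from a bootstrap that resamples subjects. Report the within-subject association of the imaging feature with GI and with GCF volume over induction and resolution.
- **Bleeding comparison.** Keep it, described as a check that the model worked.
- **Conduct.** Reconcile the visit descriptions into one order with imaging before probing and sampling, the same at every visit. Read coded images without clinical scores and, as far as registration allows, without quadrant or visit.

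The cost is SAP text, some visit re-ordering and file coding, with no added participants, visits or measurements. The intervals will be wider than those of a table that ignores clustering.
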